180 glucose and insulin sensitivity (HOMA-IR), at 3, 6 and 12 months between the vagus nerve
181 cryoablation group and the lifestyle intervention monotherapy group.
182

183 The primary safety endpoint of the trial is occurrence of death and all procedure related
184 complications, such as bleeding, infection, pneumothorax, hemothorax, pulmonary injury,
185 complications of sedation, pain requiring hospital admission or treatment, dysphagia,
186 gastroparesis, nausea and vomiting, and gastrointestinal ulceration for the duration of the study.
187

188 Secondary outcomes include differences between treatment groups in any of the following
189 measures:

- 190 1. Body mass index (BMI), waist circumference, and waist-to-hip ratio at 3 and 6 months
191 compared to baseline
- 192 2. Lipids (total cholesterol, LDL, triglycerides) at 6 months compared to baseline
- 193 3. Systolic and diastolic blood pressure at 3 and 6 months compared to baseline
- 194 4. Daily caloric intake as measured by 3-day food recall compared to baseline at 3 and 6
195 months.
- 196 5. Changes in antihyperglycemic medication regimen compared to baseline at 3 and 6
197 months.
- 198 6. Appetite, hunger and satiety scoring by visual analog scale at baseline, 1 week, 1 month,
199 3 months and 6 months
- 200 7. Physical activity questionnaire (IPAQ) at baseline, 3 and 6 months
- 201 8. Fasting glucose and insulin levels at 3 and 6 months compared to baseline

202 203 **C. STUDY DESIGN:**

204 This is a randomized, controlled, unblinded clinical study in obese adult patients with T2D,
205 HbA1c 7.5-10.5%, BMI 30-40 kg/m² treated with non-insulin antidiabetic medications with

207 stable doses for at least 3 months.

208 Subjects will be pre-screened with the relevant questions from the Three Factor Food
209 Questionnaire by phone or in person to determine eligibility prior to consent. Following consent
210 and screening for trial eligibility, subjects will be randomized to treatment group. The primary
211 endpoint, glycemic control, will be assessed at 6 months post-procedure. Patients will be
212 recruited from the diabetes clinic at Grady Memorial Hospital and Emory University Clinics.
213

[figure not shown]
214 We will be screen up to 40 participants to be able to randomized 30 patients, they will be
215 enrolled in this pilot exploratory study. Patients will be randomly allocated to undergo either CT

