216 guided cryoablation of the vagus nerve plus lifestyle intervention or lifestyle intervention alone.

217 **Group 1:** CT guided cryoablation of the vagus nerve plus lifestyle intervention (n=15).

218 **Group 2:** Lifestyle intervention by trained RD/CDE (n=15).

219 All subjects will have the procedure performed at Grady Memorial Hospital or Emory University
220 Hospital Midtown or Johns Creek by trained study personnel.
221

222 The study schema is shown below. Both groups will undergo screening for eligibility followed
223 by randomization. If the subject is not fasting at time of initial consent and screening, he/she will
224 be brought back for a subsequent visit with fasting blood work. Subjects must be randomized
225 within 4 weeks of the screening visit. If the randomization visit falls outside of the 4 week time
226 frame, the subject must undergo repeat screening procedures. In- person lifestyle counseling will
227 be provided at baseline visit for both groups. Those undergoing cryoablation will receive a phone
228 call 24 hour post-procedure to evaluate for any immediate complications, 1 week in person
229 follow up visit, as well as a safety call at 2 months. Subjects in both groups will have weekly
230 contact with RD and in person follow up visits at 4 weeks, 3 months, and 6 months. Blood work,
231 anthropometric data and questionnaires will be administered at baseline, 3 months, and 6 months.
232 Safety follow up appointments will be scheduled at 9 months and 12 months, though no further
233 lifestyle counseling will be provided after 6 months. Questioning regarding adverse events and
234 side effects will occur at all visits, as well as assessment of glycemic control. Anti-
235 hyperglycemic medications will be adjusted at visits under the direction of the endocrinologist,
236 or as needed for clinically significant hypo- or hyperglycemic events.

237
238

239 Blood work will be as follows: For all lab parameters, subject results must be within the
240 reference range unless otherwise specified by inclusion/exclusion criteria or if assessed by study
241 physician to be not clinically significant.

Lab test	Baseline	3 months	6 months	9 months	12 months
Complete metabolic panel	X	X	X	X	X
Pregnancy test	X	X	X	X	
HbA1c	X	X	X	X	X
Lipid panel	X		X		
Insulin level	X	X	X		X
TSH	X				

242
243

D. STUDY PROCEDURE:

244 **Cryoablation procedure (to be performed by [name] or [name]):** Subjects will

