21. History of autonomic dysfunction, including amyloidosis, Parkinson's disease, autoimmune disease, spinal cord injury

G. STATISTICAL CONSIDERATIONS:

464 The primary outcome is the difference in glycemic control (as measured by HbA1c) at 6 and 12
465 months between the vagus nerve cryoablation group and the lifestyle intervention group.
466 Summary statistics including mean, median, and standard deviations for the changes in HbA1c
467 at 3, 6, 9 and 12 months will be computed. We will then compare the changes at 6 months
468 between the two treatment groups by a nonparametric Wilcoxon test or a two-sample t-tests
469 (with appropriate data transformation if needed). We will conduct one-way ANOVA to estimate
470 the mean difference in glycemic parameters at 6 and 12 months month between the two
471 treatment groups. We may further adjust for some important confounders by using linear
472 regression models. We will also assess the glycemic control outcomes simultaneously across
473 different follow-up visits (i.e. 12, 24 weeks) through repeated measures ANOVA models, which
474 appropriately account for within-subject correlations in the measurements. In addition, we will
475 consider repeated measures linear regression model with visits incorporated as a continuous time
476 variable. We may include other covariates in the model when feasible.

477 The primary safety endpoint of the trial is the occurrence of death and all procedure related
478 complications, such as bleeding, infection, pneumothorax, hemothorax, pulmonary injury,
479 complications of sedation, pain requiring hospital admission or treatment, dysphagia,
480 gastroparesis, nausea and vomiting, and gastrointestinal ulceration for the duration of the study.
481 We will first use the Chi-square test (or Fisher's exact test) to compare the occurrence of this
482 primary safety endpoint between the two treatment groups. We will perform logistic regression
483 to evaluate the group difference while adjusting for other potential confounders such as age,
484 gender, and BMI. In addition, we will compare the number of procedure related complications
485 by using Poisson regression or Negative Binomial regression between the two treatment groups.
486 Standard model selection (e.g. forward, backward variable selection) and model checking
487 procedures (e.g. deviance residual plot and Hosmer- Lemeshow test) will be performed to ensure
488 the adequacy of the final models.

489

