490 Secondary outcomes will be compared between the two treatment groups. For continuous
491 secondary outcomes, we will follow the plan proposed for primary outcome. For discrete
492 secondary outcomes, we will first conduct cross-sectional comparisons based on Chi-squared
493 tests or Fisher's exact test. If the discrete outcome is measured at multiple visits, we will fit
494 repeated measures generalized linear models to simultaneously assess the difference in the
495 longitudinal discrete outcome between the two treatment groups. Other covariates may be
496 included in the models if feasible.

497

498 **Sample Size Calculation and Power Analysis:**

499 This study is generating pilot data for utilization of this procedure in a novel patient population.
500 Given the 15 patients per group, taking into account 20% attrition rate, we would have 12
501 patients per group. In this case, we would have 80% power to detect a difference in glycemic
502 control outcome change that equals 1.2 times the standard deviation of the glycemic control
503 outcome change. The data generated from this study will provide useful relevant preliminary
504 data for planning larger randomized studies.

505

506

507

IV. DATA HANDLING AND RECORD KEEPING:

508 Data collection records with personal identifiers will be stored in locked file cabinets. Blood
509 samples drawn in conjunction with this study will not be labeled with information that could
510 directly identify study subjects. De-identified serum samples will be stored. We may use the
511 samples collected and stored in this study for future studies without a separate IRB consent for
512 the subjects. This will be explained to the study subjects at the time of consent. If we use the
513 samples in future studies, coded identifiers will be used. The informed consent will make it clear
514 that subjects can request their samples to be destroyed at any time. Presentation of the study
515 results at regional or scientific meetings or in publications will not identify subjects. Access to
516 research and confidential records will be limited to clinical investigators, research coordinators,
517 and the IRB at Emory University.
518

519 Study coordinators and/or investigators will collect baseline and follow up data, complete the
520 CRF (case report form) and enter data into RedCap (electronic database provided by the Emory
521 Research Information Technology Department). Baseline data will include demographics

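### The first 6-month HbA1c test can use only patients with a 6-month value, no missing-data rule is given, and arm-dependent dropout could bias the estimate in either direction

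*Combined protocol and SAP*

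**What the plan says.** Section III.C fixes the time point: the primary "endpoint, glycemic control, will be assessed at 6 months post-procedure. Patients will be" recruited from the named clinics. Section III.G says that summaries of HbA1c change "at 3, 6, 9 and 12 months will be computed. We will then compare the changes at 6 months" and continues "between the two treatment groups by a nonparametric Wilcoxon test or a two-sample t-tests".

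The sample-size paragraph reads "Given the 15 patients per group, taking into account 20% attrition rate, we would have 12", then "patients per group. In this case, we would have 80% power to detect a difference in glycemic", then "control outcome change that equals 1.2 times the standard deviation of the glycemic control" outcome change.

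Further analyses follow the first test: one-way ANOVA, optional covariate adjustment by linear regression, and an assessment across "different follow-up visits (i.e. 12, 24 weeks) through repeated measures ANOVA models, which" account for within-patient correlation. A repeated-measures regression with continuous time is only to be considered. Continuous secondary outcomes follow the same plan.

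No analysis set, intention-to-treat statement, imputation rule or other missing-data rule appears. The laboratory table in Section III.C schedules HbA1c at baseline and at 3, 6, 9 and 12 months. Sections III.C and III.D describe the trial as unblinded. Section III.E withdraws patients with a Grade 3 to 5 adverse event. It encourages them to keep appointments for adverse-event monitoring, but does not say whether HbA1c is still measured or used.

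**The concern.** A Wilcoxon or t-test on the 6-month change needs an observed 6-month HbA1c. Unless values are imputed, and no imputation is described, a patient without one drops out of the comparison. Anyone who gave a 3-month sample and then left, or who missed month 6 and came back later, has relevant HbA1c data that this test ignores.

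Two things are at stake. The lesser is precision. The greater is that the estimate describes patients who stayed, not the arms as randomised. Patients know their allocation and only one arm has an invasive procedure, so the reasons for leaving may differ between arms and may relate to response. The results are meant to help plan larger randomised studies, so a biased effect size would carry forward into the next sample size.

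**Working it through.** **Inputs from the documents.** 15 randomised per arm, 20% attrition, 12 per arm remaining, 80% power, difference of 1.2 SD of the change (III.G); HbA1c at baseline and 3 months before the 6-month draw (III.C).

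**Inputs assumed.** Two-sided alpha of 0.05; correlation rho between 3- and 6-month change of 0.3 to 0.9; all, half or none of the dropouts having a 3-month value; the dropout mechanisms in step 4. The documents give none of these.

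**1. The plan's own figure.** 15 × 0.8 = 12 per arm. For a two-sample t-test the noncentrality is 1.2 / √(2/12) = 2.94 on 22 degrees of freedom, and power is 80.2%. The stated 80% reproduces. With the Wilcoxon test at an efficiency of 0.955, power is about 78.2%.

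**2. What attrition costs.** With 15 per arm, power at 1.2 SD would be 88.7%. The loss is 88.7 − 80.2 = 8.5 points, which the plan has already allowed for.

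**3. What 3-month values could recover.** If n3 patients per arm have a 3-month value and 12 have a 6-month value, the effective sample size per arm is

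n_eff = 1 / [rho²/n3 + (1 − rho²)/12].

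For example, with n3 = 15 and rho = 0.7: 1 / (0.49/15 + 0.51/12) = 13.3. Power at 1.2 SD, with 22 degrees of freedom:

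| rho | n_eff, all dropouts have a value (n3 = 15) | Power, all | Power, half (n3 = 13.5) | Power, none |
|---|---|---|---|---|
| 0.3 | 12.2 | 80.9% | 80.6% | 80.2% |
| 0.5 | 12.6 | 82.2% | 81.3% | 80.2% |
| 0.7 | 13.3 | 84.1% | 82.3% | 80.2% |
| 0.9 | 14.3 | 86.6% | 83.8% | 80.2% |

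The gain is 0 to about 6 points. The formula is a large-sample one that ignores the cost of estimating the regression from 12 patients, so these gains are slightly favourable.

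**4. Bias.** Simulation with a true difference of 1.20 SD, 20% dropout per arm and rho of 0.5 to 0.7. Selective dropout depends on the 3-month change through a logistic slope of 1.5 per SD.

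| Who leaves | Completers' estimate (SD) | Estimate using the 3-month value (SD) |
|---|---|---|
| At random in both arms | 1.20 | 1.20 |
| Poor responders, cryoablation only | 1.32 to 1.36 | 1.20 |
| Poor responders, lifestyle only | 1.09 to 1.04 | 1.20 |
| Poor responders, both arms alike | 1.20 | 1.20 |
| Poor responders from cryoablation, good responders from lifestyle | 1.43 to 1.52 | 1.20 |

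With no true effect and 15 per arm, of whom 3 leave, the two-sided type I error of the completers' t-test is 6% to 7% when selective dropout is confined to one arm. It is 9% to 14% in the opposite-direction case.

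The last column is unbiased because dropout was made to depend only on an observed 3-month value that every patient had. It does not cover losses before month 3 or dropout driven by unseen values.

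**5. An extreme case.** If the 3 cryoablation dropouts had no benefit over control and lifestyle dropout were uninformative, 1.2 SD in completers would be 1.2 × 12/15 = 0.96 SD in all randomised, an overstatement of 1.2/0.96 − 1 = 25%.

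**6. Effect on the next trial.** Required size scales with 1/d². At a fixed SD, an estimate of 1.32 to 1.36 would give (1.20/1.32)² = 83% to (1.20/1.36)² = 78% of the size needed. An estimate of 1.09 to 1.04 would give (1.20/1.09)² = 121% to (1.20/1.04)² = 133%.

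**The case against.** Nothing in the documents restricts the analysis to completers. The 12 per arm is a sample-size allowance, not a definition of the analysis set, and Section III.G lists several analyses without labelling one test as the sole primary. This stands: a reader might infer a declared completers-only policy, but the text supports only that the first test needs a 6-month value and that nothing is said about patients without one.

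The plan already includes repeated-measures analyses, and fitted by likelihood these could use a 3-month value when the 6-month one is missing. That also stands, but only in part. The ANOVA is an additional analysis, and in its classical form it drops incomplete patients; the regression is only to be considered. Neither is named as the primary estimate, so they do not close the gap.

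A reader might also infer that six dropouts with usable earlier HbA1c will be thrown away. Only baseline HbA1c is certain for everyone. A 3-month value exists only for those who reach that visit, and the 20% attrition is not dated within a follow-up of 12 months, so some losses may fall before month 3 or after month 6.

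Two further readings fail. Power is not overstated, since the 80% is calculated after attrition. Nor must the effect be inflated: disappointed lifestyle patients may leave too, which pulls the estimate the other way, and the 25% figure needs the specific conditions in step 5. One route to arm-specific loss does stand in the text: Grade 3 to 5 adverse events lead to withdrawal, and procedure-related ones can arise only in the cryoablation arm. The documents do not show which way this would move HbA1c.

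Finally, this is a 30-patient exploratory pilot, and a mixed model brings choices that a t-test does not. That is a fair cost, but those choices can be fixed in advance.

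**Conclusion.** The point holds as a gap in the primary analysis. The first 6-month comparison cannot use patients without a 6-month HbA1c, the trial plans on having about 12 of 15 per arm, and no rule covers the rest. A better method is available from samples already scheduled.

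The power consequence is small: 0 to about 6 points above a correctly stated 80%, depending on rho and on how many dropouts have a 3-month value. The bias consequence is more serious but of unknown sign. Under the assumed one-arm mechanisms a true 1.20 SD becomes about 1.3 to 1.4 SD or about 1.0 to 1.1 SD, and there is no bias if selective dropout is alike in both arms. Alpha, rho, the timing of attrition and the dropout mechanism are all assumptions. The change should be made before analysis, but the gap does not invalidate the design.

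**What to change.** State in Section III.G that the primary estimate is the between-arm difference in HbA1c at 6 months from a likelihood-based repeated-measures mixed model. Specify:

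- every randomised patient with any post-baseline HbA1c, in the assigned arm;
- visit as a categorical factor with a visit-by-arm term, and baseline HbA1c as covariate;
- a small-sample degrees-of-freedom correction, such as Kenward–Roger;
- the covariance structure, with a fallback named in advance. An unstructured matrix over 3, 6, 9 and 12 months has 4 × 5 / 2 = 10 parameters, which is demanding in 30 patients.

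Add one sensitivity analysis in which missing 6-month values in the cryoablation arm are imputed from the control arm. This includes patients lost before month 3, whom the model cannot use. Keep the t-test or Wilcoxon test as supportive, and report by arm how many patients lack a 6-month value and how many of those have a 3-month value.

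The cost is SAP wording, a little programming and reliance on a covariance model in a small sample. No new data are needed.
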